## **List of Tables**

**Table 1. Protocol Activities**

**Table 2. Study-Specific AE Reporting Timeline**

## PROTOCOL SYNOPSIS

Sponsor: American Sleep Medicine Foundation
Name of Finished Product: N/A
Study Title: The Clinical Utility of DLMO in the Treatment of Delayed Sleep-Wake Phase Disorder: A Randomized Trial
Study Phase: 3
Primary Objective: The objective of the proposed study is to evaluate the clinical utility of obtaining field-based dim light melatonin onset (DLMO) to time melatonin administration for patients with delayed sleep-wake phase disorder. Note that the efficacy of the intervention used to time the administration of melatonin is being tested, not the efficacy of melatonin per se.
Study Design: The study is a randomized, controlled, parallel double-blind 4-week trial of 0.5 mgs of exogenous melatonin timed to either 3 h before actual dim light melatonin onset (DLMO) based on in-home measurement (M-DLMO, n = 25) or 3 h before DLMO estimated at 2 h before average sleep onset time based on actigraphy and sleep diary (E-DLMO, n = 25) in adult participants with delayed sleep-wake phase disorder. All participants will receive melatonin 0.5 mgs. Outcomes include change in DLMO, subjective and objective sleep parameters, and daytime symptoms.
Study Population: Adults 18-65 years of age who meet diagnostic criteria for current delayed sleep-wake phase disorder.
Diagnosis and Main Criteria for Inclusion: To be enrolled in the study, participants must be 18-65 years of age, and meet diagnostic criteria for delayed sleep-wake phase disorder (DSWPD) per the International Classification of Sleep Disorders-3 (ICSD-3). Diagnostic criteria include: (1) have evidence of a delayed phase of the sleep-wake pattern on daily sleep diaries and actigraphy maintained for at least 7 days (e.g., a $\geq$ 2 h delay in the timing of habitual sleep episode between work/school and free days); (2) report difficulty falling asleep and difficulty awakening at desired/required times for $\geq$ 3 months.
Test Product; Dose; and Mode of Administration: Melatonin; 0.5 mgs; oral fast dissolve
Reference or Placebo Therapy; Dose; and Mode of Administration: N/A (all participants will receive melatonin 0.5 mgs).
Duration of Treatment: 4 weeks (28 days)
Variables: Time of DLMO in minutes; Epworth Sleepiness Scale score (ESS); Multidimensional Fatigue Inventory score (MFI-20); Short-Form Health Survey (SF-12);

from diary and actigraphy: total sleep time, initial sleep latency, sleep onset time, sleep offset time.

**Statistical Methods:** Statistical analyses will include 2-tailed t-tests and linear mixed models to test group differences on outcomes.

## 1 INTRODUCTION

### 1.1 Indication

Treatment of delayed sleep-wake phase disorder by timing melatonin administration to either measured or estimated dim light melatonin onset.

### 1.2 Background and Rationale

#### **Delayed sleep-wake phase disorder is common and debilitating**

The most common circadian rhythm sleep-wake disorder, delayed sleep-wake phase disorder (DSWPD) is estimated to affect up to 7-16% of adolescents and young adults, and more than 10% of patients presenting to sleep clinics with insomnia symptoms (American Academy of Sleep Medicine 2014). The prototypical patient with delayed sleep-wake phase disorder presents with chronic difficulty falling asleep and waking at required or socially desired times (American Academy of Sleep Medicine 2014). When free to select their own sleep schedule, patients with DSWPD have significantly later sleep onset and wake times relative to convention, with preserved sleep quality and normal sleep duration (American Academy of Sleep Medicine 2014). Delay of the circadian timing system relative to the required or socially desired timing of the sleep episode is posited to be one of the major etiological factors (Micic et al. 2016). This is corroborated by numerous studies, which show delays ranging from 2-6 h in DSWPD patients' circadian phase relative to normal sleepers (Oren et al. 1995, Ozaki et al. 1996, Shibui et al. 1999, Uchiyama et al. 2000, Watanabe et al. 2003).

The inability to maintain a sleep-wake schedule consistent with social and occupational requirements often leads to chronic sleep loss and significant daytime impairments. Consequences of DSWPD are wide-ranging and include absenteeism and presenteeism, and impairment in social and family life (Rajaratnam et al. 2015). Indeed, role disability is greater, and quality of life is more impaired, in adults with DSWPD relative to other chronic disorders, including sleep apnea, migraine, and depression (Nagtegaal et al. 2000).

#### **Effective treatment of DSWPD is challenging under current treatment paradigms**

Despite its prevalence, treatment of DSWPD is challenging. Effective treatment requires correcting the circadian phase so that it is optimally aligned with the desired sleep-wake schedule. Treatment options include light therapy, hypnotic medications, prescribed sleep-wake scheduling, timed physical activity, and wakefulness promoting medications. Among the available treatment options, the American Academy of Sleep Medicine (AASM) Clinical Practice Guideline for treatment of DSWPD in adults recommends only one therapy: timed exogenous melatonin (Auger et al. 2015). As noted in both the Clinical Practice Guideline and its accompanying editorial, there is a significant lack of research on clinical populations with circadian sleep-wake rhythm disorders, and treatment of circadian rhythm sleep-wake disorders such as DSWPD, with a particular need for field-based studies (Auger et al. 2015). Previous placebo-controlled studies of melatonin for DSWPD in adults show improvements in objectively measured sleep parameters, including increased total sleep time, reduced sleep onset latency, advanced DLMO time, and an advanced time of sleep onset time for melatonin relative to placebo (Kayumov et al. 2001, Mundey et al. 2005, Rahman et al. 2010).

However, on average, these improvements are relatively modest and development of treatment protocols that enhance the efficacy of melatonin therapy is needed. Clinical strategies that allow for home-based measurement of DLMO and the administration of melatonin personalized to each patient's DLMO hold promise to improve the efficacy of melatonin. Indeed, evidence from laboratory-based studies of healthy adults suggests that melatonin must be administered at the correct time in the phase response curve relative to the individual's circadian phase to achieve a shift in circadian timing ([name] et al. 2008, [name] et al. 2010). One previous study has demonstrated the importance of the timing of melatonin administration in maximizing phase advances in adults with DSWPD, with a more robust phase advance observed for earlier administration times (Mundey et al. 2005). Nevertheless, to date, no study has evaluated the clinical superiority of timing the administration of melatonin to an individual's circadian time vs. clock time using a randomized design.

### **Dim light melatonin onset can be readily measured in the field**

The time of melatonin onset in dim light (or dim light melatonin onset; DLMO) is the gold standard circadian marker (Lewy et al. 1989) and most reliable circadian phase marker in humans (Klerman et al. 2002). Dim light melatonin onset can be obtained via blood, urine, or saliva; advantages of saliva relative to other methods include practicality and reliability (Benloucif et al. 2008). Historically, research utilizing DLMO has been conducted in laboratory settings, which limits clinical utility. However, our group has pioneered the development of, and established the validity for, a kit for home-based saliva sampling to measure DLMO in the field. [name] (Co-I) has developed a novel in-home DLMO kit, which she has validated against laboratory DLMOs, with a very high correlation between the in-home and in-laboratory DLMOs ( $r = 0.91$ ,  $p < 0.001$ ), and excellent compliance, as 92% of the in-home samples were valid ([name] et al. 2015). Crucially, [name] has also validated the kit in adults with DSWPD, with high correlations ( $r = 0.93$ ,  $p < 0.001$ ) relative to in-laboratory DLMOs and high compliance, as 83% of the in-home samples were valid ([name] et al. 2016). In conjunction with [name], [name] (PI) has used the in-home DLMO kit with postpartum women with depression, with excellent compliance (98% of the DLMOs were valid; ([name] et al. 2017)).

### **Objective of the proposed study**

The objective of the proposed study is to evaluate the clinical utility of obtaining field-based DLMO in the treatment of DSWPD using a randomized controlled study design. Our central hypothesis is that timing exogenous melatonin administration using measured DLMO will result in a more robust treatment response after 4 weeks of therapy relative to timing exogenous melatonin administration using an estimation of DLMO. The rationale for the proposed project lies in the critical need to understand whether use of objective circadian markers, particularly field-based markers, enhances treatment outcomes in DSWPD to reduce the burden of this circadian rhythm sleep disorder. This proposal leverages our unique expertise with field-based, validated in-home assessment of DLMO and clinical treatment of DSWPD. We plan to test our central hypothesis with a double-blind randomized trial of measured DLMO (M-DLMO,  $n = 25$ ) vs. estimated DLMO (E-DLMO,  $n = 25$ ) for timing exogenous melatonin administration in adults with DSWPD.

### **1.3 Hypothesis**

#### Specific Aims

Aim 1: Compare pre- to post-treatment changes in DLMO in M-DLMO vs. E-DLMO conditions.

Hypothesis 1: Participants in the M-DLMO condition will show greater improvements in DLMO (i.e., greater advance of DLMO) relative to participants in the E-DLMO condition after 4 weeks of exogenous melatonin.

Aim 2: Compare pre- to post-treatment changes in objective and subjective sleep parameters and daytime symptoms in M-DLMO vs. E-DLMO conditions.

Hypothesis 2: Participants in the M-DLMO condition will show greater improvements in objective (per wrist actigraphy) and subjective (per daily sleep-wake diary) sleep parameters (specifically, total sleep time, initial sleep latency, sleep onset time, sleep offset time) after 4 weeks of exogenous melatonin. They will also show greater improvements in daytime symptoms.

### **1.4 Previous Human Experience**

Melatonin is designated as a dietary supplement by the FDA. A recent, randomized, double-blind clinical trial to assess the toxicology of chronic melatonin tested 10 mg of oral melatonin administered daily for 28 days (n = 30) versus placebo (n = 10) in healthy adults (Seabra et al. 2000). Measurements included the following laboratory tests: complete blood count, urinalysis, sodium, potassium and calcium levels, total protein levels, albumin, blood glucose, triglycerides, total cholesterol, high-density lipoprotein (HDL), low-density lipoprotein (LDL), and very low-density lipoprotein (VLDL), urea, creatinine, uric acid, glutamic-oxalacetic transaminase phosphate, gama-glutamic transaminase, T3, T4, TSH, LH/FSH, cortisol, and melatonin serum concentrations. Additional measurements included the Epworth Sleepiness Scale, and participants were also asked about side effects. No toxicological changes were noted in participants in the melatonin group. There were no differences between melatonin and placebo on any of the laboratory tests or Epworth Sleepiness Scale. There were no differences between melatonin and placebo in side effects. The most common side effects reported in the melatonin group included somnolence and headache.

Other studies in healthy adults have investigated psychomotor performance and melatonin. One of the studies examined the effects of 5 mg of oral melatonin vs. placebo on driving performance using a randomized, placebo-controlled, double-blind, crossover design in 20 healthy adults (Suhner et al. 1998). Measures included a medical examination, subjective sleepiness, body sway measurement, and a standardized driving computer battery (which tested attention, reaction time, power of concentration, and sensomotor coordination). All measures were administered 60 minutes after the melatonin was ingested. No differences were observed between melatonin and placebo on any of the driving performance measures, although subjective sleepiness was greater in the melatonin group vs. placebo. A second study evaluated the psychomotor effects of time-release oral melatonin 6 mg in 23 healthy adults; measures included serial reaction time, logical reasoning, serial subtraction, and

multitask (Paul et al. 2003). Participants completed testing 7 hours after ingestion of melatonin. Melatonin did not impair performance on any task.

Melatonin has also been investigated in human clinical populations. A recent randomized, double-blind, placebo-controlled study of oral melatonin 6 mg vs placebo, taken daily for 3 months, on depression symptoms in adult females who were undergoing surgery for breast cancer found that melatonin reduced depressive symptoms, and there were no differences on side effects between the groups (Hansen et al. 2014). In a randomized, double-blind, placebo-controlled trial of 12 weeks of oral melatonin 3 mg (60 participants) vs. placebo (59 participants) and amitriptyline 25 mgs (59 participants) for the prevention of migraine headaches in adults, participants in the melatonin group reported a similar rate of side effects/adverse events to placebo, with the most common side effect of sleepiness; further, melatonin was equal, or superior to, amitriptyline on the migraine endpoints (Goncalves et al. 2016). In a trial of 1 or 3 mg of oral melatonin vs. placebo nightly for 12 months in 81 postmenopausal women with osteopenia, melatonin was not different from placebo with respect to side effects/adverse events; further, no hangover effect affecting balance- and muscle function was found following the intake of melatonin (Amstrup et al. 2015).

Melatonin has also been studied in adult humans as a treatment of delayed sleep-wake phase disorder (the indication for the present study). One of the earliest randomized controlled, trials was a crossover study conducted in 8 adults with delayed sleep wake phase syndrome, which evaluated oral melatonin 5 mgs vs placebo nightly for 4 weeks. Results indicated that melatonin was produced at a significantly earlier sleep onset time and wake time relative to placebo, with no next-day hangover effects (Dahlitz et al. 1991). Later randomized, controlled trials in adults with delayed sleep-wake phase syndrome have demonstrated the efficacy of melatonin for this disorder, including: 20 participants randomized to 4 weeks of nightly oral melatonin 5 mg or placebo, which found that melatonin produced improvements in sleep onset latency, with no difference from placebo in sleepiness, fatigue, and alertness (Kayumov et al. 2001); 30 participants in a crossover trial studying 2 weeks of nightly 5 mg oral melatonin vs. placebo, showing that melatonin produced significant advancement of the endogenous melatonin profile, advance of sleep onset, and shortened sleep latency (Nagtegaal et al. 1998); in 20 participants in a crossover trial of 4 weeks of nightly oral melatonin (5 mg) or placebo, melatonin improved sleep continuity and depression symptoms (Rahman et al. 2010); and for 13 participants who were randomized to 4 weeks of nightly oral melatonin (0.3 or 3 mg) or placebo, melatonin (regardless of dose) advanced the circadian phase of exogenous melatonin and sleep onset (Mundey et al. 2005). The dose of melatonin (0.5 mgs) was selected based on work by [name] (Co-I; ([name] et al. 2010)) and others (Mundey et al. 2005), which has shown similar phase shifting effects between smaller (0.3-0.5 mgs) and larger (3.0 mg) doses. As earlier administration produces maximal phase shifts, we propose to use the lowest effective dose to minimize possible soporific effects of taking melatonin during waking hours.

## 2 STUDY OBJECTIVES AND ENDPOINTS

### 2.1 Objectives

The objective of the proposed study is to evaluate the clinical utility of obtaining field-based DLMO in the treatment of DSWPD using a randomized controlled study design. Our central

hypothesis is that timing exogenous melatonin administration using measured DLMO will result in a more robust treatment response after 4 weeks of therapy relative to timing exogenous melatonin administration using an estimation of DLMO. The rationale for the proposed project lies in the critical need to understand whether use of objective circadian markers, particularly field-based markers, enhances treatment outcomes in DSWPD to reduce the burden of this circadian rhythm sleep disorder. This proposal leverages our unique expertise with field-based, validated in-home assessment of DLMO and clinical treatment of DSWPD. We plan to test our central hypothesis with a double-blind randomized trial of measured DLMO (M-DLMO, n = 25) vs. estimated DLMO (E-DLMO, n = 25) for timing exogenous melatonin administration in adults with DSWPD.

## **2.2 Endpoints**

Endpoints were selected to include those identified as “critical” and “important” by the AASM Clinical Practice Guideline (Auger et al. 2015).

### **2.2.1 Primary Endpoint**

The primary endpoint is change in time of DLMO from pre- to post-treatment.

### **2.2.2 Secondary Endpoint**

Secondary endpoints include:

- Change in sleep parameters per wrist actigraphy and sleep diary (specifically, total sleep time, initial sleep latency, sleep onset time, sleep offset time) from pre- to post-treatment.
- Change in daytime symptoms and functioning (as assessed by the Epworth Sleepiness Scale, Multidimensional Fatigue Inventory-20, Sheehan Disability Scale, Patient Health Questionnaire-9, Generalized Anxiety Disorder-7) from pre- to post-treatment.
- Change in self-report sleep quality and symptoms (as assessed by the Pittsburgh Sleep Quality Index, Morningness Eveningness Questionnaire, PROMIS-Sleep Disturbance scale, PROMIS-Sleep Related Impairment scale).

## **3 STUDY DESIGN**

### **Overview of research design**

This study is a randomized, controlled, parallel double-blind 4-week trial of 0.5 mg of exogenous melatonin (Emens et al. 2015) timed to either 3 h before actual DLMO based on in-home measurement (M-DLMO, n = 25) or 3 h before DLMO estimated at 2 h before average sleep onset time based on actigraphy and sleep diary (E-DLMO, n = 25). Note that the intervention tested is the method used to time melatonin administration--not melatonin per se, as all participants will receive the same dose of melatonin for the duration of the study.

## **4 SUBJECT SELECTION**

### **4.1 Subject Recruitment**

Fifty participants will be recruited over 2 years. Recruitment will occur within the greater Ann Arbor community, the Michigan Medicine Behavioral Sleep Medicine (BSM) clinics,

affiliated with the Michigan Medicine Sleep Disorders Center, where Drs. [name] (PI), [name] (Co-I), and [name] (Co-I) provide direct clinical care, and the University of Michigan's University Health Service (UHS) Collegiate Sleep Disorders Clinic (CSDC), directed by [name] (Co-I). The UHS provides health care to all students enrolled at University of Michigan (> 40,000 students). Between the CSDC and BSM Clinics, an average of 63 new patients are seen per month, 8 of whom are diagnosed with DSWPD. Thus, we anticipate a pool of at least 95 patients annually from which we will recruit to meet our enrollment target of 25 participants per year.

#### ***4.1.1 Inclusion Criteria***

1. 18-65 years of age
2. ICSD-3 diagnosis of DSWPD: (1) have evidence of a delayed phase of the sleep-wake pattern on daily sleep diaries and actigraphy maintained for at least 7 days (e.g., a  $\geq 2$  h delay in the timing of habitual sleep episode between work/school and free days); (2) report difficulty falling asleep and difficulty awakening at desired/required times for  $\geq 3$  months.
3. Female participants of childbearing potential (i.e., they are not permanently sterilized (hysterectomy, bilateral salpingectomy and bilateral oophorectomy) or postmenopausal (12 months with no menses without an alternative medical cause) by report) must agree to use a reliable method of contraception from the screening visit until 4 weeks after the study has completed. Acceptable methods of birth control during participation in the study include: oral contraceptives, patch contraceptives, injection contraceptives, male condom with spermicide, diaphragm or cervical cap with spermicide, vaginal contraceptive ring, intrauterine device, surgical sterilization (bilateral tubal ligation), vasectomized partner(s), or total sexual abstinence.

#### ***4.1.2 Exclusion Criteria***

1. Hypersensitivity to melatonin or any other component of the product
2. Suspicion of a sleep disorder other than DSWPD per interview (Edinger et al. 2004) and medical record review (when available)
3. Presence of chronic psychiatric conditions which may directly influence sleep per interview and medical record review (when available), including:
  - current illicit drug use,
  - current alcohol or drug abuse,
  - bipolar disorder,
  - psychotic disorder.
4. Presence of unstable chronic medical condition which may directly influence sleep (e.g., chronic pain, thyroid conditions)
5. Current or past history of medical conditions which may affected by melatonin per self-report and medical record review (when available), such as
  - Hypertension or hypotension
  - diabetes,
  - clotting/bleeding disorders,
  - epilepsy/seizures,
  - autoimmune disorders,
  - conditions requiring immunosuppressive management such as transplant.

6. Per self-report or medical record review (when available), current use of medications which may have interactions with melatonin:
  - nifedipine,
  - anti-hypertensive medications (including, but not limited to, chlortalidone, chlorothiazide, hydrochlorothiazide, indapamide, metolazone, Lisinopril, Benazepril, captopril, candesartan, losartan, amlodipine, diltiazem);
  - immunosuppressants (including, but not limited to, prednisone, budenoside, prednisolone, cyclosporine, tacrolimus, sirolimus, everolimus, azathioprine, leflunomide, mycophenolate);
  - sedative or hypnotic medications (including, but not limited to, zolpidem, suvorexant, butabarbital, quazepam, estazolam, flurazepam, triazolam, eszopiclone, temazepam, secobarbital, doxepin, zaleplon);
  - antidiabetes drugs (including, but not limited to, insulin, metformin, glyburide, glipizide, glimepiride, repaglinide, nateglinide, rosiglitazone, pioglitazone, canagliflozin, dapagliflozin, liraglutide);
  - anticoagulant/antiplatelet (including, but not limited to, heparin, warfarin, rivaroxaban, dabigatran, apixaban, edoxaban, enoxaparin, fondaparinux, clopidogrel, ticagrelor, prasugrel, dipyridamole, dipyridamole/aspirin, ticlodipine, eptfibatide.)
  - CYP4501A2 strong or moderate inhibitors or inducers (including, but not limited to, fluoroquinolones such as ciprofloxacin, fluvoxamine, verapamil, St. John's wort, modafinil, nafcillin, omeprazole)
7. Pregnancy (as determined by urinary pregnancy test at screening for women of child-bearing potential) or self-report of breastfeeding
8. Self-report of routine night shift work
9. Self-report of past month travel or planned travel during the study across more than one time zone
10. Self-report of use of melatonin in the past month
11. Current use of medications that may interfere with the measurement of melatonin (NSAIDs if used daily, and beta-blockers, (Benloucif et al. 2008)) per self-report and medical record review (when available)

## 5 STUDY TREATMENTS

### 5.1 Allocation to Treatment

Eligible participants will be randomized using the minimization method (Pocock et al. 1975) in a 1:1 ratio to M-DLMO or E-DLMO. Assignment to condition will be balanced by age and baseline sleep onset time on free days. For allocation of participants, a computer program (the Treatment Assignment System, created by UM's Consulting for Statistics, Computing, and Analytics Research) will be used by the study coordinator to generate the group assignment at enrollment for each participant.

Participants will be blinded to the specific study hypotheses and to their group assignment. The study clinician will be blinded to group assignment. The study coordinator, who communicates the time of melatonin administration to the study clinician, will not be blinded to the actual DLMO of participants in the M-DLMO condition; however, they will be blinded to the actual DLMO of participants in the E-DLMO condition until their participation is complete.

Due to individual variation in melatonin levels or errors in the saliva collection process, it is possible that DLMO will not be able to be determined for a small proportion of participants. To retain these participants in the protocol, if they are randomly assigned to the M-DLMO condition, the study coordinator may change their assignment to the E-DLMO condition. Data for these participants will be examined post-hoc upon completion of the study using sensitivity analyses before determining whether to retain or discard their data from analyses.

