### **6.2 Treatment Study Period**

#### **Visit 1 (Day 1)**

Participants will have their first session with the study clinician at Visit 1. Prior to the session, study staff will meet with the participant to download their actigraphy. Study staff will provide the study clinician with the initial clock time at which each participant should take melatonin. The initial clock time of melatonin administration for participants assigned to the M-DLMO condition will be set at 3 h before their measured baseline DLMO. The initial clock time of melatonin administration for participants assigned to the E-DLMO condition will be set at 5 h before their average time of sleep onset at baseline per most recent 7 days of actigraphy. Participants be provided with a 14-day supply of melatonin 0.5 mgs, which they will begin taking that evening.

During the first visit, study staff will query whether participants have had any changes in their medications or medical history since the screening, and review concomitant medications. Participants' baseline sleep diary and actigraphy data will be reviewed by the study clinician. The study clinician will provide them with specific instructions regarding when to take melatonin, their bed time, their wake time, and when to dim ambient lighting and electronic devices to their lowest usable level (timed to be approximately 60 minutes before their scheduled bedtime). They will be provided with a handout summarizing this information.

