## 7.1 Primary Endpoint Assessments

Protocol activity and assessments are summarized in Table 1 above.

Primary endpoint: change in the time of DLMO from pre- to post-treatment.

To assess time of DLMO, all eligible participants (regardless of group assignment) will undergo in-home salivary DLMO collection at pre- and post-treatment, using the protocol established by [name] (Co-I) ([name] et al. 2015). Participants will be oriented to the collection procedures during their clinic visit. Participants will be in dim light starting 30 minutes prior to the first sample collection. Collection begins 6 hours prior to participants' habitual sleep onset per their most recent week of actigraphy at baseline. At post-treatment, collection begins 6 hours prior to participants' bed time as assigned at the final treatment session. Samples are collected via Salivette every 30 minutes until bedtime (13 samples total). They are provided with a kit, which includes: a checklist of procedures; a test tube rack; a toothbrush; a nightlight; blue-blocking Uvex glasses (with an Actiwatch attached to monitor compliance of use); an iPod programmed to alarm at collection times; a light medallion (an Actiwatch with light sensor worn around the neck to monitor compliance with light exposure); Salivette collection vials equipped with Track Cap, which will record when the vial was opened; and a label dispenser with pre-labeled labels. Participants wear the blue-blocking glasses throughout the dim light saliva collection and are required to remain seated in the 10 minutes before each sample. When the iPod alarms, participants brush their teeth without toothpaste, collect saliva by chewing on the Salivette, and deposit it in the vial. Participants are informed about the compliance measures utilized in the study. Samples will be stored in participants' freezers until they can be transported to our facility. Samples are centrifuged for two minutes, frozen, and assayed using Bühlmann Laboratory radioimmunoassay (ALPCO Diagnostics, Salem, NH) at **Solidphase Inc.** To ensure consistency and to minimize the effects of sleep schedule changes on the weekends/days off of work, whenever possible, all participants will complete DLMO collection on the third night of their typical workday sleep schedule (e.g., DLMO collection will occur on a Wednesday, Thursday, or Friday night for participants who work a traditional Monday-Friday schedule).

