### **9.2 Data Analysis**

Descriptive analyses will be completed by graphical and numerical summarization of key variables. Treatment groups will be compared on pre-treatment demographic and clinical variables using t-tests, chi-square tests, and Fisher's exact tests as appropriate. Variables that emerge as potential confounders from this analysis will be controlled for in the final analyses. Weekly averages will be calculated for total sleep time, initial sleep latency, sleep onset time, and sleep offset time for each week of the study for both actigraphy and sleep diary.

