#### ***9.2.1 Analysis of Primary Endpoint***

Change in DLMO from pre- to post-treatment will be calculated in minutes for each participant. A 2-tailed t-test will evaluate the difference between the change in DLMO between the two groups.

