#### ***9.2.2 Analysis of Secondary Endpoints***

Linear mixed models using a repeated measures group X time (weeks of study) model will be used to determine between-group main effects and interactions with week of study for the following actigraphy and sleep diary variables: sleep onset time, initial sleep latency, total sleep time, sleep offset time, wake after sleep onset, and sleep efficiency. T-tests (2-tailed) will compare group differences in the change from pre- to post-treatment on the following: ESS score; SF-12 score; MFI-20 score.

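### Section 5.1 allows M-DLMO participants without a determinable DLMO to be moved to E-DLMO but fixes neither their analysis arm nor a criterion for keeping their data, which can bias the secondary (Aim 2) comparisons

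*Combined protocol and SAP*

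**What the plan says.** Section 5.1 (Allocation to Treatment) expects that "DLMO will not be able to be determined for a small proportion of participants", because of individual melatonin levels or errors in saliva collection. For these participants, "if they are randomly assigned to the M-DLMO condition, the study coordinator may change their assignment to the E-DLMO condition". After the study is complete their data are to be examined "using sensitivity analyses before determining whether to retain or discard their data from analyses". No criterion for that decision is given, and no analysis arm is named.

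The reason for the move is practical. Under Visit 1 (Day 1), the M-DLMO administration time "will be set at 3 h before their measured baseline DLMO", so without a measured value that arm has no starting time.

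The analysis sections do not close the gap. Section 9.2 says "Variables that emerge as potential confounders from this analysis will be controlled for in the final analyses" but defines no analysis set. Section 9.2.1 says "Change in DLMO from pre- to post-treatment will be calculated in minutes for each participant". Section 9.2.2 uses group-by-week mixed models for the actigraphy and diary variables, and for the questionnaires "T-tests (2-tailed) will compare group differences in the change from pre- to post-treatment". None of these sections says whether a moved participant counts as M-DLMO or E-DLMO.

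**The concern.** Participants can move in one direction only. If they are kept in E-DLMO, that arm holds the undeterminable participants of both arms and M-DLMO holds none (assuming every permitted move is made). If only the moved participants are dropped, M-DLMO loses its undeterminable participants while E-DLMO keeps its own. In both cases the groups compared are no longer the randomised groups.

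This matters for Aim 2, whose actigraphy, diary and questionnaire endpoints need no DLMO value, so moved participants have usable data. If they change differently over treatment, a difference between arms can appear without any effect of timing. In the mixed models, a difference in level is enough to affect the group main effect. In the change-score t-tests a stable difference in level cancels, and only a difference in change matters. One of the causes that Section 5.1 names, individual melatonin levels, makes a prognostic difference plausible, but the documents do not show one.

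**Working it through.** **1. Handlings left open.** Section 5.1 and Sections 9.2 to 9.2.2, read together, allow at least four:

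- (a) keep everyone, with moved participants counted as E-DLMO, which is what changing the assignment suggests;
- (b) discard only the moved participants;
- (c) exclude undeterminable participants from both arms;
- (d) analyse everyone as allocated.

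Section 5.1 does not make clear whether the retain-or-discard decision covers only those who moved or also E-DLMO participants without a determinable DLMO. So (b) and (c) are both possible.

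**2. Inputs.** The plan gives no figure of its own to reproduce here.

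- Planned size: 25 per group (Section 9.1).
- Validity rates (Section 1.2): 83% in adults with DSWPD, 92% in the first kit validation, 98% in postpartum women. Only the last is worded as a share of DLMOs; the other two are shares of samples. They are a loose proxy for the share of participants with a determinable DLMO.
- Assumed: undeterminable participants do worse by g = 0.5 SD (0.25 SD as a check). The documents give no value.
- Assumed: no timing effect, and every permitted move is made.

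**3. Expected composition.** With f = 1 − valid = 0.17 / 0.08 / 0.02:

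- Expected number moved = 25f = 4.25 / 2.0 / 0.5.
- Under (a), the undeterminable share of E-DLMO = 50f / (25 + 25f) = 8.5/29.25, 4/27, 1/25.5 = 0.291 / 0.148 / 0.039. In M-DLMO it is 0.
- Under (b), the share is f in E-DLMO and 0 in M-DLMO.
- Under (c) it is 0 in both arms. Under (d) it is f in both arms.

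**4. Expected bias** = difference in share × g. With g = 0.5 SD:

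| Handling | 83% valid | 92% valid | 98% valid |
|---|---|---|---|
| (a) kept as moved | 0.145 SD | 0.074 SD | 0.020 SD |
| (b) only the moved discarded | 0.085 SD | 0.040 SD | 0.010 SD |
| (c) excluded from both arms | 0 | 0 | 0 |
| (d) as allocated | 0 | 0 | 0 |

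With g = 0.25 SD, handling (a) gives 0.073 / 0.037 / 0.010 SD. With g = 0 there is no bias.

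**5. Type I error** of a two-sided pooled t-test at 0.05. Simulation with 25 per arm, binomial failures, SD 1 and no timing effect; 400,000 trials per setting for (a), (c) and (d), with Monte Carlo standard error about 0.0004. With g = 0.5 SD:

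| Handling | 83% valid | 92% valid | 98% valid |
|---|---|---|---|
| (a) kept as moved | 0.0754 | 0.0565 | 0.0502 |
| (c) excluded from both arms | 0.0501 | 0.0501 | 0.0496 |
| (d) as allocated | 0.0498 | 0.0501 | 0.0496 |

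Handling (b) gives about 0.059 at 83% (8,000 trials; standard error √(0.059 × 0.941 / 8,000) ≈ 0.003). With g = 0.25 SD, handling (a) gives 0.056 / 0.051 / 0.050. The mixed models were not simulated.

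**6. Primary endpoint.** The Section 9.2.1 change score needs a pre-treatment DLMO. A participant whose baseline DLMO cannot be determined has no change score in either arm, whether moved or not. The consequence is a loss of numbers, not a bias from the move.

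**The case against.** The plan is open about these participants, commits to examining them and expects few of them. The trigger is a failed measurement, not an outcome, and collection errors need not be prognostic. Section 9.2 also adjusts for baseline variables that emerge as confounders. All of this stands and keeps the problem modest. The adjustment is only partial mitigation, since it works through measured variables that happen to differ between the groups.

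The size is assumed twice: the deficit is not in the documents, and the validity rates are a proxy. At 98%, the only rate worded as DLMOs, the effect is negligible. This stands as well.

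A reader might infer that the planned sensitivity analyses would fail to catch the bias. The documents do not support that, because they state no rule. If the rule were to discard whenever inclusion changes the conclusion, the result would always equal that of symmetric exclusion: where the two analyses agree nothing changes, and where they disagree the symmetric one is used. Type I error would then be about 0.05. Other rules would behave differently. Whether the planned analyses remove the bias cannot be judged from the text. What remains is that a choice of data set made after completion has no stated criterion.

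It could also be said that changing the assignment settles the analysis arm as E-DLMO. The plan does not say so, and if it did, that is the most biased of the four handlings.

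**Conclusion.** The gap is real: a one-directional move after randomisation, no stated analysis arm, and no criterion for keeping or dropping the data. Two of the four open handlings can bias the Aim 2 comparisons and two do not.

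On the assumptions above, the effect of keeping participants as moved is visible at 83% valid, small at 92% and negligible at 98%. These figures illustrate the mechanism for t-tests and do not predict the trial's error rate. The direction is unknown, so nothing here shows that M-DLMO would be favoured. A reader might extend the point to the primary endpoint, but the change score's need for a baseline DLMO rules that out.

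This is a cheap improvement to the plan, not a flaw that threatens its main result.

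**What to change.** Leave the timing these participants receive to the investigators, and keep the sentence that governs it. Add to Section 5.1 that a change in timing does not change the analysis arm. Replace the retain-or-discard sentence, and repeat the rule in Section 9.2:

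1. All participants are analysed in the arm allocated by the minimisation program.
2. Participants without a determinable baseline DLMO are handled alike in both arms: not evaluable for the primary change score, and included as randomised for the secondary endpoints.
3. One prespecified sensitivity analysis excludes them from both arms alike. It is reported beside the main analysis and not used to choose it.

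Point 3 is feasible because under Section 7.1 "all eligible participants (regardless of group assignment) will undergo in-home salivary DLMO collection at pre- and post-treatment", and the coordinator's blinding to E-DLMO values ends once participation is complete (Section 5.1).

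The cost is wording only: no added participants or procedures, and no change to anyone's timing. The downside is some dilution on the secondary endpoints. If measured timing does nothing for these participants, the as-allocated effect is (1 − f) of the full effect, about 83% / 92% / 98%. The symmetric sensitivity analysis shows the undiluted contrast.
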